# **11 APPENDICES**

# **11.1 Quality of Life Derivation**

#### 11.1.1 SF-36 Scoring Information

Derivation of summary scores, including appropriate handling of missing items, will be performed using the scoring software provided by the owner of the scale (Optum software, owned by QualityMetric®). Details of the specific derivations are held by QualityMetric.

The SF-36 (v2.0) consists of 36 items, as follows:

- 1:In general, would you say your health is
- 2: Compared to one year ago, how would you rate your health in general now
- 3A: Vigorous activities, such as running, lifting heavy objects, participating in strenuous sports
- *3B:Moderate activities, such as moving a table, pushing a vacuum cleaner, bowling, or playing golf*
- *3C:Lifting or carrying groceries*
- 3D: Climbing several flights of stairs
- 3E:Climbing one flight of stairs
- 3F:Bending, kneeling, or stooping
- 3G: Walking more than a mile
- 3H: Walking several hundred yards
- 31: Walking one hundred yards
- 3J:Bathing or dressing yourself
- 4A:As a result of your physical health, cut down on the amount of time you spent on work or other activities
- 4B:As a result of your physical health, accomplished less than you would like
- 4C:As a result of your physical health, were limited in the kind of work or other activities
- 4D:As a result of your physical health, had difficulty performing the work or other activities (for example, it took extra effort)
- 5A:As a result of any emotional problems, cut down the amount of time you spent on work or other activities
- 5B:As a result of any emotional problems, accomplished less than you would like
- 5C:As a result of any emotional problems, did work or other activities less carefully than usual
- 6:During the past 4 weeks, to what extent has your physical health or emotional problems interfered with your normal social activities with family, friends, neighbors, or groups
- 7: How much bodily pain have you had during the past 4 weeks
- 8:During the past 4 weeks how much did pain interfere with your normal work (including both work outside the home and housework)

- 9A: How much of the time during the past 4 weeks: did you feel full of life
- 9B:How much of the time during the past 4 weeks: have you been very nervous
- 9C:How much of the time during the past 4 weeks: have you felt so down in the dumps that nothing could cheer you up
- 9D:How much of the time during the past 4 weeks: have you felt calm and peaceful
- 9E:How much of the time during the past 4 weeks: did you have a lot of energy
- 9F:How much of the time during the past 4 weeks: have you felt downhearted and depressed
- 9G: How much of the time during the past 4 weeks: did you feel worn out
- 9H:How much of the time during the past 4 weeks: have you been happy
- 91: How much of the time during the past 4 weeks: did you feel tired
- 10:During the past 4 weeks, how much of the time has your physical health or emotional problems interfered with your social activities (like visiting your friends, relatives, etc.)
- 11A: I seem to get sick a little easier than other people
- 11B:I am as healthy as anybody I know
- 11C:I expect my health to get worse
- 11D:My health is excellent

From the responses to these questions, the physical component score (PCS) and mental component score (MCS) are derived from the following subscores:

Scale	Item	Coding	Range of Raw	Normalization*
			Score	
Physical	Items 3a to 3j	Yes, limited a lot $= 1$	10 (Worst) – 30	(S-10)/20x100
Functioning		Yes, limited a little $= 2$	(Best)	
		No, not limited $= 3$		
Role-	Items 4a to 4d	All of the time $= 1$	4 (Worst) – 20	(S-4)/16x100
Physical		Most of the time $= 2$	(Best)	
		Some of the time $= 3$		
		A little of the time $= 4$		
		None of the time $= 5$		
Bodily Pain	Item 7	None = 6	2 (Worst) – 12	(S-2)/10x100
		Very Mild = 5.4	(Best)	
		Mild = 4.2		
		Moderate = 3.1		
		Severe = 2.2		
		Very Severe = 1		
	Item 8 if both	Not at all and Item 7 is		
	items 7 and 8	"None" = 6		
	are answered	Not at all and Item 7 is not		
		"None" = 5		

Scale	Item	Coding	Range of Raw Score	Normalization*
		A little bit = 4		
		Moderately $= 3$		
		Quite a bit $= 2$		
		Extremely $= 1$		
,	Item 8 if item 7	Not at all $= 6$	1	
	is not answered	A little bit $= 4.75$		
		Moderately $= 3.5$		
		Quite a bit $= 2.25$		
		Extremely $= 1$		
General	Item 1	Excellent = 5	5 (Worst) – 25	(S-5)/20x100
Health		Very good = $4.4$	(Best)	
		Good = 3.4		
		Fair = 2		
		Poor = 1		
	Items 11a and	Definitely true = 1	-	
	11c	Mostly true $= 2$		
		Don't know = 3		
		Mostly false = 4 Definitely		
		false = 5		
	Items 11b and	Definitely true = 5 Mostly	1	
	11d	true = 4		
		Don't know = $3$		
		Mostly false $= 2$		
		Definitely false $= 1$		
Vitality	Items 9a and 9e	All of the time $= 5$	4 (Worst) – 20	(S-4)/16x100
		Most of the time $= 4$	(Best)	
		Some of the time $= 3$		
		A little of the time $= 2$		
		None of the time $= 1$		
	Items 9g and 9i	All of the time $= 1$		
	_	Most of the time $= 2$		
		Some of the time $= 3$		
		A little of the time $= 4$		
		None of the time $= 5$		
Social	Item 6	Not at all $= 5$	2 (Worst) – 10	(S-2)/8x100
Functioning		Slightly $= 4$	(Best)	
		Moderately $= 3$		

Scale	Item	Coding	Range of Raw	Normalization*
		Ouite a hit = 2	Score	
		Quite a $Dit = 2$		
		Extremely = 1	-	
	Item 10	All of the time $= 1$		
		Most of the time $= 2$		
		Some of the time $= 3$		
		A little of the time $= 4$		
		None of the time $= 5$		
Role-	Items 5a to 5c	All of the time = 1	3 (Worst) – 15	(S-3)/12x100
Emotional		Most of the time $= 2$	(Best)	
		Some of the time $= 3$		
		A little of the time $= 4$		
		None of the time $= 5$		
Mental	Items 9b, 9c and	All of the time = 1	5 (Worst) – 25	(S-5)/20x100
Health	9f	Most of the time $= 2$	(Best)	
		Some of the time $= 3$		
		A little of the time $= 4$		
		None of the time $= 5$		
	Items 9d and 9h	All of the time $= 5$		
		Most of the time $= 4$		
		Some of the time $= 3$		
		A little of the time $= 2$		
		None of the time $= 1$		

Note: \* S = raw score = sum of item scores after coding

Each scale score is then standardized based on the latest US population figures (held by Optum) to produce the following standardized Scale Scores:

- Physical Functioning
- Role-physical
- Bodily pain
- General health
- Vitality
- Social functioning
- Role-emotional
- Mental heath

Finally, the SF-36 PCS and MCS transformed scores are derived. Additionally, norm-based transformation of the 8 scale scores will occur.

#### **11.1.2 Multidimensional Assessment of Fatigue (MAF)**

The items of the MAF will be scored as follows (per American College of Rheumatology guidance):

- Items 1, 4 14: 10pt scale from 1 = 'not at all' to 10 = 'a great deal'
- Item 2: 10pt scale from 1 = 'mild' to 10 = 'severe'
- Item 3: 10pt scale from 1 = 'no distress' to 10 = 'a great deal of distress'
- Timing items 15 and 16: Categorical responses: 1 to 4
- To calculate the Global Fatigue Index (GFI), convert item 15 to a 0 10 scale by multiplying each score by 2.5 and then sum items 1, 2, and 3, and average 4 14, and newly scored item 15. Do not assign a score to items 4 14 if the respondent gave a response of "do not do any activity for reasons other than fatigue." If a respondent selects "no fatigue" on item 1, assign a zero to items 2 16. Item 16 is not included in the GFI.

A higher score indicates more severe fatigue, fatigue distress, or impact on activities of daily living.

# 11.1.3 EQ-5D

The EQ-5D is a standardized PRO for use as a general measure of health outcome. The EQ-5D has 5 questions used to create a descriptive "health state" and a VAS to capture a patient's overall health rating. The 5 questions and derivation of the total score are as follows. Additionally, the 5 questions will be mapped to an index value using the crosswalk link function based on the published EQ-5D-5L Crosswalk Index Value Set.

Question	Coding
Mobility (EQ5D0201)	I have no problems walking = 1
	I have slight problems walking = 2
	I have moderate problems walking' = 3
	I have severe problems walking = 4
	I am unable to walk $= 5$
Self-Care	I have no problems washing and dressing myself = 1
(EQ5D0202)	I have slight problems washing and dressing $myself = 2$
	I have moderate problems washing and dressing $myself = 3$
	I have severe problems washing and dressing $myself = 4$
	I am unable to wash and dress myself = $5$

Question	Coding	
Usual Activities	I have no problems doing my usual activities = 1	
(EQ5D0203)	I have slight problems doing my usual activities $= 2$	
	I have moderate problems doing my usual activities = 3	
	I have severe problems doing my usual activities = 4	
	I am unable to do my usual activities $= 5$	
Pain/Discomfort	I have no pain or discomfort = 1	
(EQ5D0204)	I have slight pain or discomfort $= 2$	
	I have moderate pain or discomfort $= 3$	
	I have severe pain or discomfort = 4	
	I have extreme pain or discomfort $= 5$	
Anxiety/Depression	I am not anxious or depressed = 1	
(EQ5D0205)	I am slightly anxious or depressed $= 2$	
	I am moderately anxious or depressed $= 3$	
	I am severely anxious or depressed = 4	
	I am extremely anxious or depressed $= 5$	
EQ-5D Total Score	Determine 'health state' which for example if all questions were	
	answered '1' then it would be	
	11111 per participant per visit where:	
	• EQ5D0201 outcome x 10000	
	• EQ5D0202 outcome x 1000	
	• EQ5D0203 outcome x 100	
	• EQ5D0204 outcome x 10	
	• EQ5D0205 outcome x 1	
EQ-5D Index	Corresponding index value from the US country value set from the	
	Euroquol list, based on the 'health state'. The crosswalk value set	
	can be found here .	

Version 4.0: 22 Feb 2024

Version 4.0: 22 Feb 2024

[figure not shown]

Version 4.0: 22 Feb 2024

[figure not shown]

-	

Version 4.0: 22 Feb 2024

[figure not shown]

[figure not shown]

Version 4.0: 22 Feb 2024

[figure not shown]

[figure not shown]

[figure not shown]

[figure not shown]

[figure not shown]

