• To compare Chronocort to IRHC in terms of the impact on quality of life (QoL) using the self-completed Medical Outcome Study 36-Item Short Form Health Survey (SF- 36 ® ) total score and the sub-domain of vitality.	• The change from baseline to 4, 10, 16 and 28 weeks of randomized treatment in QoL using the self-completed SF-36® total score and the sub-domain of vitality will be summarized and compared between treatment arms.
• To compare Chronocort to IRHC in terms of the impact on QoL using the Multidimensional Assessment of Fatigue (MAF).	• The change from baseline to 4, 10, 16 and 28 weeks of randomized treatment in QoL using the MAF will be summarized and compared between treatment arms.

 
To compare Chronocort to IRHC in terms of the impact on QoL using the 5-level Standardized Health Questionnaire (EQ-5D-5LTM).
 
	• The change from baseline to 4, 10, 16 and 28 weeks of randomized treatment in QoL using the EQ-5D-5L ™ will be summarized and compared between treatment arms.
Compliance	
• To assess compliance over the study period.	• The percentage overall treatment compliance will be summarized.
Exploratory Efficacy	

Version 4.0: 22 Feb 2024

Safety	•
• To assess the safety and tolerability of Chronocort relative to IRHC.	• The incidence, nature, severity, relatedness, duration, outcome, seriousness and expectedness of treatment emergent adverse events (TEAEs) will be tabulated by treatment arm. AEs of special interest will additionally be tabulated separately, with particular note of adrenal crises.
• To assess the need for use of additional glucocorticoid doses (stress dosing rules).	• The use of medication from the stress dosing packs or use of any additional glucocorticoid treatment during the study will be tabulated by treatment arm.
• To evaluate the safety of Chronocort compared to IRHC by assessment of routine safety laboratory assessments, physical examination, vital signs, and electrocardiogram (ECG).	• Safety hematology, biochemistry, urinalysis, and vital signs conducted at each post-randomization visit and the physical examination and ECG assessments conducted after 28 weeks of randomized treatment, and their changes from baseline, will be summarized by treatment arm.

 This description aligns with the ICH E9 requirement for the definition of an Estimand. Outcome variables are underlined

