# 5.2.4 Quality of Life: SF-36, MAF, EQ-5D

QoL questionnaires (SF-36®, MAF, and EQ-5D-5LTM) will be completed by the participants at Visits 2, 3, 4, 5 and 6 through an electronic data collection tool. No missing data will be allowed by the system and therefore no missing data imputation method will be needed.

The scores for the SF-36 questionnaire for each domain and total will be calculated using the Optum software. The total scores for MAF and EQ-5D will be derived programmatically as per their respective user guides. See Section 11.1 for further details of derivation.

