#### 5.3.2 Decimal Places

Decimal places for derived data described in Section 5.2 will be determined by the scale of measurement unless otherwise stated. No decimal places will be displayed if the smallest calculated value is  $\geq$  100; 1 decimal place will be displayed when the smallest value is within the interval (10, 100), with 10 being inclusive; 2 decimal places will be displayed when the smallest value is within (1, 10), with 1 being inclusive; and so on for even smaller scales of measurement.

Derived data where it is known in advance the result will be an integer, for example day, month, year, number of days and total scores (for rating scales) will be presented with zero decimal places.

Means, medians and percentiles will be displayed to one more decimal place than the data, dispersion statistics (e.g. standard deviation) will have two more decimal places, and the minimum and maximum will be displayed to the same number of decimal places as reported in the raw data. Percentages will be displayed with one decimal place.

P-values will be quoted to 3 decimal places. P-values < 0.001 will be presented as "p<0.001". Where this value is less than 0.05 (two-sided test), 0.025 (one-sided test), 0.01 or 0.001, attention will be drawn to this fact using the conventional "\*", "\*\*" or "\*\*\*" annotation, respectively. These conventions will be footnoted in the table or figure shell.

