# 5.11.6.2 Standard Methodology for Comparisons of Other Secondary Efficacy Endpoints

Unless otherwise stated, continuous outcome variables will be compared between treatment arms using analysis of covariance (ANCOVA) adjusting for the standard explanatory variables. Unless otherwise stated, a treatment policy approach will be assumed for all ICEs, with no imputation of missing data. If a non-normal distribution is anticipated or observed, then consideration will be given to using a logarithmic transformation or a non-parametric analysis. Analyses of change from baseline will always include the baseline value as a covariate. Example code is provided in Section 11.4.

Unless otherwise stated, binary outcome variables will be compared between treatment arms using logistic regression adjusted for the standard explanatory variables. Unless otherwise stated, a treatment policy approach will be assumed for all ICEs, with non-responder imputation of

missing data. The procedure described by Ge et al. (2011) will be used to estimate the standard error and resulting confidence interval around the covariate adjusted difference in proportions

Outcome Variables	Outline Analyses
Whether or not the participant is a biochemical	The same analysis will be used as for the primary
responder at 4, 10 and 16 weeks after	estimand of the primary outcome variable (except
randomization.	that at 4 weeks there has been no opportunity for a
	dose titration so the condition on dose is not used).
Whether or not the participant is a dose	The same analysis will be used as for the primary
responder at 10 and 16 weeks after	estimand of the first key secondary outcome
randomization.	variable.
Total daily dose at 10 and 16 weeks after	The same analysis will be used as for the primary
randomization.	estimand of the second key secondary outcome variable.
Whether or not the participant is in biochemical	The same analysis will be used as for the primary
control (provided total daily dose is not greater	estimand of the primary outcome variable.
than 30mg) at 4, 10, 16 and 28 weeks after	
randomization.	
The difference in range as calculated as the	Standard methodology for comparisons.
difference between the 08:00 and 13:00 17-OHP	
levels at 4, 10, 16 and 28 weeks after	
The difference in range as calculated as the	Standard methodology for comparisons.
difference between the 08:00 and 13:00 A4	
revers at 4, 10, 10 and 28 weeks after	

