weeks of randomized treatment in QoL using the MAF The change from baseline to weeks 4, 10, 16 and 28 in subjective hirsutism and acne using a participant-reported VAS.	Standard methodology for comparisons (women only).

Outcome Variables	Outline Analyses
The change from baseline to weeks 4, 10, 16	Standard methodology for comparisons.
and 28 in QoL using the EQ-5D-5L ™ .	

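### Will the EQ-5D-5L be compared as a five-digit health-state code, and is the SF-36 total left undefined?

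*SAP*

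**What the plan says.** **EQ-5D.** SAP Section 5.2.4 states: "The total scores for MAF and EQ-5D will be derived programmatically as per their respective user guides". It refers the reader to Section 11.1 for the derivations. Section 11.1.3 introduces its table with "The 5 questions and derivation of the total score are as follows". The row labelled as the total score sets out five weighted terms, starting with "EQ5D0201 outcome x 10000" and falling by a factor of ten to a weight of 1, and it calls the result a health state. The following row takes the index value from the US value set on the basis of that health state. The introduction also mentions a visual analogue scale (VAS).

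In SAP Section 5.11.6.3 the endpoint row ends "and 28 in QoL using the EQ-5D-5L" and assigns the standard methodology. For continuous variables, Section 5.11.6.2 makes that an analysis of covariance with the baseline value as a covariate. Protocol Section 9.4.2.4 likewise names no particular EQ-5D quantity.

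**SF-36.** SAP Section 2 defines the endpoint by its "total score and the sub-domain of vitality will be summarized and compared between treatment arms". Section 5.2.4 says: "The scores for the SF-36 questionnaire for each domain and total will be calculated using the Optum software". Section 11.1.1 lists eight scale scores, their norm-based versions, and the physical and mental component scores. It adds that the owner of the instrument holds the exact derivations.

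**The concern.** Read literally and in sequence, Section 5.2.4 derives an EQ-5D total score, Section 11.1.3 defines that total as the health-state code, and Section 5.11.6.3 applies an analysis of covariance to change in the EQ-5D-5L. A programmer who followed that chain could put the code into the model. The digits of a code have no common unit, so its mean, its change from baseline and its adjusted treatment difference would have no meaning. The result would also follow mobility almost alone if mobility varies about as much as the other items do.

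For the SF-36, a reader of Section 11.1.1 cannot see which listed output is the total named in the endpoint. If the compared variable is open for either instrument, it could in principle be chosen after unblinding.

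**Working it through.** **1. Reproduce the SAP's own example.** The weights in Section 11.1.3 are 10,000, 1,000, 100, 10 and 1. With every item answered 1, the code is 10,000 + 1,000 + 100 + 10 + 1 = 11,111, as the SAP states.

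**2. Test the code as a score.**
- One level worse on mobility adds 10,000; one level worse on anxiety/depression adds 1.
- State 21111 has level sum 2 + 1 + 1 + 1 + 1 = 6. State 15555 has level sum 1 + 5 + 5 + 5 + 5 = 21.
- The code ranks the milder state as worse: 21,111 − 15,555 = 5,556.

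**3. How general is this?** Five items with five levels give 5^5 = 3,125 states and 3,125 × 3,124 / 2 = 4,881,250 pairs. Of these, 4,454,340 pairs differ in level sum, and the code reverses the order in 1,306,185. That is 29.3% of untied pairs, or 26.8% of all pairs. This weights every state equally and takes the unweighted level sum as the yardstick. Both are assumptions.

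**4. Weight of mobility.** Assume independent items, with the other four sharing one SD and mobility's SD equal to r times it. Mobility's share of the code's variance is r²·10^8 / (r²·10^8 + 10^6 + 10^4 + 10^2 + 1).

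| r | Calculation | Mobility share |
|---|---|---|
| 1 | 100,000,000 / 101,010,101 | 99.0% |
| 0.5 | 25,000,000 / 26,010,101 | 96.1% |
| 0.1 | 1,000,000 / 2,010,101 | 49.7% |
| 0 | 0 / 1,010,101 | 0% |

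The documents give no item SDs, so this shows only a range. Steps 2 to 4 show that the code is unfit as an outcome. They do not show that the plan uses it as one.

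**5. Does any passage put the code into a comparison?**
- Section 5.2.4 belongs to the section on derived data. It says what is computed, not what is compared, and its reference to Section 11.1 takes in the index as well.
- Section 11.1.3 calls the number a health state and uses it in the next row to find the index. A lookup key is a valid use of the code.
- Section 5.11.6.3 and Protocol Section 9.4.2.4 name the instrument only.
- Section 5.3.2 says that "total scores (for rating scales) will be presented with zero decimal places". This is a general rule for results known in advance to be integers, and it does not mention the EQ-5D. It cannot be describing all the quality-of-life totals: in Section 11.1.2 the fatigue index adds item 15 multiplied by 2.5, so a response of 1 contributes 2.5.
- Section 5.11.6.2 refers to example code in Section 11.4. Those pages are not readable in the public copy, so silence in the visible text is not silence in the plan.

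**6. SF-36.** Sections 5.2.4 and 11.1.1 agree that the scoring is left to the owner's software. They differ only in that 5.2.4 mentions a total and 11.1.1 does not list one. The documents do not show whether the software returns a total. The other half of the endpoint, vitality, is fully specified: items 9a, 9e, 9g and 9i, raw range 4 to 20, rescaled as (S − 4)/16 × 100.

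**7. What depends on it?** Section 5.11.8 confines formal testing to the primary and two key secondary endpoints and treats all other secondary analyses as descriptive, without multiplicity adjustment.

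**The case for a change.** The strongest opposing case is that a plan should not need a sensible reader. Section 5.2.4 names a total score and not the index, and it does so alongside the fatigue total, which is a genuine numeric scale. The table attaches the words *total score* to a number that is not a score. Both quality-of-life measures are named secondary endpoints with planned between-arm comparisons, and a few words in the SAP would close the question before unblinding. That the example code might settle the matter does not correct the label.

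Much of this stands. The label is wrong, and the visible text does not say whether the index, the VAS or both are compared. It does not stand that the plan analyses the code, because that needs a step no passage takes. The room for choice is also narrow. Once the code is read as a lookup key, the index and the VAS remain, and both are recognisable summaries that can be reported side by side. Calculated p-values for these endpoints are declared indicative in any case. For the SF-36, the component scores, the eight scales and vitality are specified whatever the total turns out to be.

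**Conclusion.** No change to the plan is called for. On the EQ-5D there is a clerical slip, the label on one row, together with a detail that analysts can be expected to fill sensibly, since the index is already derived one row below. On the SF-36 there is a small mismatch between two sections, within scoring that the SAP openly leaves to the owner's software.

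The 5,556-point reversal, the 29.3% of untied pairs and the mobility shares are all conditional on a use of the code that the documents do not state. The reversal share also rests on equal weighting of states and the level sum as yardstick; the variance shares rest on independent items and assumed SD ratios. The non-inferiority decision, the two superiority decisions and the sample size are unaffected.

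This conclusion assumes that the unreadable example code does not itself enter the health-state code as the response variable. Nothing in the visible text suggests that it does.
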